6.1.6. Pooling of Sites

Not applicable. Site will be omitted from statistical models as the anticipated number of subjects per site is small, treatment is self-administered, and the sites are using standardized procedures for all assessments. If the distribution of enrollments at sites is such that one or few are enrolling a majority of subjects, an ad hoc analysis by site may be performed.

6.1.7. Derived Variables

- IGA average score = in protocol version 1.0, IGA was assessed by body area (chest/abdomen, back, arms, and legs). Under protocol version 2.0, this was changed to a global (overall) assessment. For comparability, the average of the body area IGA results will be taken to yield one score for subjects enrolled under protocol version 1.0. Scores will range from 0 to 4. Higher scores indicate worse disease.
- VIIS total score = sum of the individual body area scaling scores, with a range of 0 to 16. Each individual item is scored on a scale of 0-4, where 0 = normal skin; no perceptible scale or smoothening and 4 = confluent, primarily large, thick scales. Higher scores indicate worse scaling.
- Ectropion total score = sum of the 8 individual item scores (lateral apposition, medial apposition, scleral show, conjunctival show, excess tear film, redness of the eye, round canthus, punctum lacrimale), with a range of 0 to 8. Each individual item is scored 0

(nonaffected/no/invisible), 0.5 (≤ 1 mm/emerging), or 1 (affected/yes/visible). Higher scores indicates worse ectropion.

- DLQI total score = sum of the 10 individual item scores, with a range of 0 to 30. Higher scores indicate poorer quality of life.
- CDLQI total score = sum of the 10 individual item scores, with a range of 0 to 30. Higher scores indicate poorer quality of life.
- Number of doses taken = total number of tubes returned – total number of tubes returned unused
- Number of weeks on study = (last day on study – treatment start date + 1) / 7
- Number of expected doses = 2 * number of weeks on study
- Total weight used = total weight of tubes dispensed (grams) – total weight of tubes returned (grams)
- Initial application amount used = tube weight before drug application (grams) – tube weight after drug application (grams), as collected on the initial study drug application CRF
- Compliance by tube weight = total weight used / total weight of tubes dispensed * 100%
- Compliance by number of doses = number of doses taken / number of expected doses * 100%
- Change from baseline = value at current time point – value at baseline.
- TEAE = An AE is defined as treatment emergent if the onset or worsening is at the time of or following the start of the first application of study drug (trifarotene or vehicle) through the Follow-up Visit or Early Termination Visit, whichever occurs first..

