6.1.4. Handling of Dropouts or Missing Data

All possible efforts will be made to ensure that subjects stay in the study and all data are collected as scheduled. Withdrawn subjects will not be replaced. If a substantial number of subjects are withdrawn from the study, the sponsor will evaluate the need for developing replacement criteria. Randomized subjects withdrawn from the study may not reenter.

Missing endpoint values in this study may result from subjects discontinuing from the study prematurely or missing intermediate assessments while remaining on study. To assess the effect of missing data on the primary efficacy analysis, a sensitivity analysis will be performed using multiple imputation (MI) for the Double-blind Period only. Multiple imputations will be used to replace missing IGA outcomes using multiple draws from the posterior predictive distribution estimated from the vehicle treatment. The IGA scores will be imputed and then categorized as treatment success.

Sensitivity analyses to investigate robustness to missing data will be performed for the primary endpoint as described in [Section 8.1.2](#).

Missing safety data and data for secondary endpoints will not be imputed.

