The change from baseline IGA score will be analyzed using a mixed model for repeated measures (MMRM). The MMRM model will include change from baseline in IGA score as the dependent variable, treatment, study visit, treatment-by-visit interaction, and age group as fixed effects, subject as a random effect, and baseline IGA score as a covariate. All post-baseline study visits will be included in the model; however, the primary comparison will be between the active trifarotene cream HE1 groups and vehicle at Day 90. An unstructured covariance matrix will be used to model the within-subject errors. The Kenward-Roger approximation will be used to estimate degrees of freedom. In case of convergence issues, other covariance structures will be explored including autoregressive (AR(1)), compound symmetry (CS), and variance components (VC) with each model fit to find the covariance structure with the best fit. The fit statistics will be compared for all covariance structures; the structure with the smallest Akaike information criterion will be retained as the preferred model and noted in the resulting table. For the OLE period, the model will not include treatment or treatment-by-visit interaction since all subjects receive the same treatment in the OLE.

The least squares (LS) mean change from baseline will be presented along with the associated 95% CI within each treatment group. The overall *P* value of the model will be presented to test

the null hypothesis that the change from baseline to subsequent study visit is 0 with a 2-sided alternative considering a difference in either direction.

In comparing treatments (active trifarotene cream HE1 groups minus vehicle), LS mean differences in change from baseline will be presented along with associated 95% CIs and *P* values. The null hypothesis that the difference in change from baseline in active trifarotene cream HE1 groups minus control vehicle is 0 with a 2-sided alternative considering a difference in either direction. Even if a difference from vehicle is observed, as described above, successful treatment is defined as clear/almost clear overall (IGA scores of 0 or 1) and at least a 2-grade change from baseline.

The observed value and change from baseline in IGA score will also be summarized descriptively by study visit and treatment group using descriptive statistics in addition to the above noted models for the Double-blind Period and OLE. Categorical IGA scores will also be presented.

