8.1.2. Multiple Imputation

Multiple imputation (MI) of the primary endpoint will be performed as an analysis of sensitivity to missing data in the Double-blind Period only. Following database lock, thorough assessment on the extent of missing data due to COVID-19 will be carried out specifically as pertains to the primary and secondary endpoints. This will inform decisions around reasonability of imputing missing data for secondary endpoints in the Double-blind Period as well. The final determination will be documented in the CSR.

MI assumes that the statistical behavior of drug- and control-treated subjects after discontinuing study drug becomes that of the vehicle group. Multiple-imputations will be used to replace missing IGA outcomes using multiple draws from the posterior predictive distribution estimated from the vehicle treatment group. IGA scores will be imputed and then categorized as treatment success according to Section 8.1.1 above. A placebo-based pattern mixture model (PMM) will be utilized following the steps outlined in Ratitch B and O’Kelly, M.J. (2011)⁴.

Data are processed sequentially by repeatedly calling SAS[®] PROC MI to impute missing outcomes at study visit $t = 1, \dots, T$. The following procedure is followed:

- *Initialization (Step 1)*. Set $t = 0$ (baseline study visit).
- *Iteration (Step 2)*. Set $t = t + 1$. Create a dataset combined records from drug- and vehicle-treated subjects with columns for covariates **X** and outcomes at study visits 1, ..., t with outcomes for all subjects set to missing at study visit t and set to observed or imputed values at study visits 1, ..., $t-1$.
- *Imputation (Step 3)*. Run placebo-based pattern mixture model in SAS[®] PROC MI on this data to impute missing values for study visit t using previous outcomes for study visit 1 to $t-1$ and baseline covariates.
 - Replace imputed data for all subjects at study visit t with their observed values, whenever available. If $t < T$ then go to Step 2, otherwise proceed to Step 4.
 - Repeat steps 1-3, m times with different seed values to create m imputed complete datasets. In this analysis, m will be assigned 50.

- *Analysis (Step 4)*. For each completed dataset use the model as it would have been applied had the data been complete for the continuous outcome. The final inference on treatment difference is conducted from the multiple datasets, as implemented in SAS[®] PROC MI ANALYZE.

The steps for this approach are detailed below:

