1. Transpose data horizontally by study visit and impute all non-monotone (intermittent) missing data using the Markov Chain Monte Carlo (MCMC) method of PROC MI. Note that this imputation will sample data within each treatment group. SAS pseudo code is provided below.

```
PROC MI DATA=example seed = 6654 NIMPUTE = 20 OUT = outdata1;  
  BY <treatment>;  
  MCMC chain=multiple impute=monotone;  
  VAR <treatment> <baseline score> <visitX score> .. <visit6 score>;  
RUN;
```

2. Using the imputed datasets from Step #1 that are now monotone missing (no intermittent missing data), a single call to PROC MI (including the MNAR statement) will be utilized to impute the monotone missing data. Within the call to PROC MI, one timepoint is imputed at a time. When imputing at time-point t , the imputation step will include all vehicle subjects, but only those from the active arms that have a value missing at time-point t . Subjects with non-missing data that are on active arms will not contribute to the estimation for this step.

Repeat the above step for all timepoints t . Thus, the data for timepoint $t+1$ uses the data imputed from previous timepoints.

SAS pseudo code is provided below. SAS accomplishes this iterative process in one step.

```
PROC MI DATA=example seed = 2617 NIMPUTE = 1 OUT = outdata1;  
  BY __imputation__;  
  CLASS <treatment>;  
  MONOTONE REG ( / details);  
  MNAR MODEL (<v1 score> .. <v6 score> /  
    modelobs=(treatment=("vehicle")));  
  VAR <baseline score> <v1 score> .. <vX score>..<v6 score> ;  
RUN;
```

3. Pass the output from Step 2 into the model by the imputation variable (coalesce into one from each step above). When all missing data are imputed, PROC MIANALYZE will be used to combine the parameters from the analyses for inference.

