The observed value and change from baseline in individual score for roughness will also be summarized descriptively by study visit and treatment group using descriptive statistics in addition to the above noted model for the Double-blind Period and OLE.

Additionally, the proportion of subjects who experience a 2-grade change from baseline to Day 90 in individual score for roughness will be summarized by treatment group and analyzed using a logistic regression model with treatment, baseline individual score for roughness, and age group as factors. The odds ratios and 95% CIs for the odds ratios will be presented. The difference in proportions between the active trifarotene cream HE1 groups and vehicle cream group, 95% CIs for the differences, and *P* values for the differences in treatment will also be presented.

The potential for heterogeneity of treatment effects will be assessed by testing treatment-by-factor interactions. The logistic regression model for the analysis will be expanded to include the treatment-by-age group interaction. In the event of quasi or complete separation, the logistic regression model will use Firth’s penalized maximum likelihood estimation.

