In comparing treatments (active trifarotene cream HE1 groups minus vehicle), LS mean differences in change from baseline will be presented along with associated 95% CIs and P values. The null hypothesis that the difference in change from baseline in active trifarotene cream HE1 groups minus control vehicle is 0 with a 2-sided alternative considering a difference in either direction.

The observed value and change from baseline in palm/sole assessment score will also be summarized descriptively by study visit and treatment group using descriptive statistics in addition to the above noted model for the Double-blind Period and OLE.

Additionally, the proportion of subjects who experience a 2-grade change from baseline to Day 90 in palm/sole assessment score will be summarized by treatment group and analyzed using a logistic regression model with treatment, baseline palm/sole assessment score, and age group as factors. The odds ratios and 95% CIs for the odds ratios will be presented. The difference in proportions between the active trifarotene cream HE1 groups and vehicle cream group, 95% CIs for the differences, and P values for the differences in treatment will also be presented.

The potential for heterogeneity of treatment effects will be assessed by testing treatment-by-factor interactions. The logistic regression model for the analysis will be expanded to include the treatment-by-age group interaction. In the event of quasi or complete separation, the logistic regression model will use Firth's penalized maximum likelihood estimation.

8.2.4. Quality of life per Dermatology Life Quality Index (DLQI) and Children's DLQI (cDLQI)

The DLQI is a dermatology-specific Quality of Life instrument for subjects aged 17 years and older. The cDLQI is for subjects aged 12 to 16 years. It is a 10-question validated questionnaire with 6 domains: symptoms and feelings, daily activities, leisure, work and school, personal relationships, and treatment. Higher scores indicate poorer quality of life. The investigator will use his or her judgment of the maturity of the subject to decide which version of the questionnaire to use; the same version will be used for the subject throughout the study.

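### The whole-grade IGA success rule is applied to quarter-step averages and continuous imputed scores with no stated mapping to grades

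*SAP*

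**What the plan says.** - **Averaged scores.** SAP Section 6.1.7 explains that version 1.0 graded the IGA in four body areas and version 2.0 changed to one global grade. For comparability, "the average of the body area IGA results will be taken to yield one score for subjects enrolled under protocol version 1.0". No rounding is mentioned.
- **Success rule.** Section 8.1.1: "successful treatment is defined as clear/almost clear overall (IGA scores of 0 or 1) and at least a 2-grade change from baseline".
- **Imputed scores.** Section 8.1.2: "IGA scores will be imputed and then categorized as treatment success according to Section 8.1.1 above". Section 6.1.4 says the same. The code imputes intermittent gaps by MCMC and monotone gaps by "MONOTONE REG ( / details", with no rounding or range option.
- **Number of imputations.** Section 8.1.2: "In this analysis, m will be assigned 50". The code in that section sets NIMPUTE to 20 in the first PROC MI call and to 1 in the second.
- **Other responders.** Section 8.2.2 analyses "the proportion of subjects who experience a 2-grade change from baseline to Day 90 in individual score for roughness". Section 8.2.3 counts subjects who "experience a 2-grade change from baseline to Day 90 in palm/sole assessment score".
- **Displays.** The categorical IGA shell has rows for 0, 1, 2, 3 and 4 only. The IGA MMRM shell prints minimum and maximum to one decimal. The SAP's only rounding rules concern P values, percentages and display precision.

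**The concern.** A score of 0.75 or 1.25 is neither 0 nor 1, and the plan does not say which side of the line it falls on. A programmer could read the rule as an average of at most 1, as exactly 0 or 1, or as the nearest grade, and these give different primary outcomes for the same subject. A version 2.0 subject graded globally from 3 to 1 is a success. A version 1.0 subject with much the same skin may not be. With 65 subjects enrolled, a few reclassifications can matter.

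In the imputation analysis the issue is mechanical. On a continuous scale, grade 1 covers roughly 0.5 to 1.5, so a cut at 1 discards about half of that band. The success rate falls for a reason that has nothing to do with missing data.

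**Working it through.** The SAP gives no figure for this point, so there is none to reproduce. The inputs are the rules above. Everything else is a labelled assumption.

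**1. Averages: worked cases** (mean = sum of four areas / 4)

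| Baseline (mean) | Day 90 (mean) | Change | Average ≤1 | Exactly 0 or 1 | Nearest grade |
|---|---|---|---|---|---|
| 3,3,3,3 (3.00) | 0,1,1,1 (0.75) | 2.25 | success | failure | success |
| 3,3,3,3 (3.00) | 1,1,1,2 (1.25) | 1.75 | failure | failure | success |
| 3,3,3,2 (2.75) | 1,1,1,1 (1.00) | 1.75 | failure | failure | success |
| 4,4,4,4 (4.00) | 0,0,0,4 (1.00) | 3.00 | success | success | success |

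In the third row every area is almost clear, yet both unrounded readings fail the subject. In the fourth, one area is still severe and the subject passes. The third row assumes that version 1.0 entry allowed a baseline average below 3; the SAP does not give that entry rule.

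**2. Averages: illustrative size.** Assume a subject who is truly almost clear at Day 90, with each area independently one grade off with probability 0.15 in each direction. Let S be the sum of the four deviations.

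- P(S = 0) = 0.7⁴ + 12 × 0.15² × 0.7² + 6 × 0.15⁴ = 0.2401 + 0.1323 + 0.0030 = 0.375
- P(average ≤1) = (1 + 0.375)/2 = 0.69
- P(S = 1) = 4 × 0.15 × 0.7³ + 12 × 0.15³ × 0.7 = 0.2058 + 0.0284 = 0.234, so P(average <1.5) = 0.688 + 0.234 = 0.92
- P(exactly 0 or 1) = 0.375 + 0.15⁴ = 0.38

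Applying the change criterion as well, with area error at both visits, a true 3-to-1 responder is scored a success as follows (total error probability per area 0.1, 0.2, 0.4):

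- average ≤1: 0.73, 0.61, 0.52
- nearest grade: 0.99, 0.96, 0.87

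A true 3-to-2 or 4-to-2 non-responder passes with probability at most 0.002 unrounded and 0.021 rounded.

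**3. Imputed scores.** A continuous draw equals exactly 0 or 1 with probability zero, so only a cut-off reading can work. Take an assumed vehicle Day 90 distribution of 5/35/30/20/10% over grades 0-4: 40% at grade 0 or 1, mean 1.95, SD 1.07.

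- P(draw ≤1) = Φ((1 − 1.95)/1.07) = 0.19
- P(draw <1.5) = Φ((1.5 − 1.95)/1.07) = 0.34

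Other shapes with 40% success give 17-21% and 34-37%. A fuller simulation (latent autoregressive scores with correlation 0.7, cut to five grades, Day 90 regressed on baseline and earlier visits) gives:

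| True vehicle success | Imputed, cut ≤1 | Imputed, rounded |
|---|---|---|
| 40% | 21% | 35-36% |
| 30% | 16% | 28-29% |
| 20% | 10% | 21% |

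**4. Effect on the treatment difference.** If the strict cut lowers imputed success by about the same amount d in both arms, the difference changes by −d × (m_active − m_vehicle), where m is the fraction missing. From the table, using the upper rounded figures, d is 36 − 21 = 15, 29 − 16 = 13 or 21 − 10 = 11 points.

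- Equal missingness: d × 0 = 0. Simulation with 20% missing per arm gave differences of 24.0-26.5 points unrounded and 24.0-26.9 rounded, a gap of at most about 1 point.
- 10% against 30% missing: 0.20 × 15 = 3.0, 0.20 × 13 = 2.6, 0.20 × 11 = 2.2 points. The direction depends on which arm loses more subjects.

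**5. Number of imputations.** 20 × 1 = 20 completed datasets against the 50 stated.

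**The case against.** Several points on the other side stand.

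- **Direction.** A reader might infer that true successes are systematically scored as failures. The documents do not support that. Averages can hide an uncleared area, and whether 1,1,1,2 is globally almost clear is a clinical judgement that the SAP does not settle. Reading the rule as an average of at most 1 is workable. Randomisation is 1:1:1 within each cohort, so a strict cut falls on all arms.
- **Imputation.** This is a sensitivity analysis, and every arm is imputed from the vehicle model, so most of the loss cancels in the contrast. The code is labelled pseudo code, so missing options are weak evidence about the final program. The text, however, supplies no mapping either.
- **Roughness and palm/sole.** A reader might infer that 4 to 1 is excluded and 2 to 4 counted as a response. That holds only if the phrase means exactly two grades in either direction. The SAP shortens such phrases elsewhere: Section 8.1.1 asks for at least a 50% reduction in IGA, while the matching shells say only 50% reduction. The wording is loose, not a demonstrated error, and these are additional analyses.
- **Baseline IGA.** Fractions would create sparse levels only if baseline is fitted as categorical. Section 8.1.1 lists it among the factors of the logistic model but as a covariate in the MMRM.
- **Rounding has a cost.** Quarter-step averages fall on .5. With halves rounded up, 2.50 to 1.25 becomes 3 to 1, a 2-grade success on a real change of 1.25.

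None of this supplies the missing rule.

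**Conclusion.** The gap is real: the primary responder variable cannot be programmed uniquely for version 1.0 subjects, and they face a different standard from later subjects. The errors run both ways. Their effect on the primary result cannot be sized, because the SAP gives neither the number of version 1.0 subjects nor how far body areas differ from a global grade. The probabilities above illustrate the mechanism and do not estimate the bias.

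In the imputation analysis, a cut at 1 or below roughly halves imputed success in each arm under the assumed distributions. It would be too strong to conclude that the treatment comparison is materially biased. The shift is near zero with equal missingness and about 2-3 points at 10% against 30%. The conflict between 50 and 20 imputations is plain from the text. The roughness and palm/sole wording needs tightening only.

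**What to change.** Before unblinding:

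1. State one mapping from averaged IGA to grades, with a rule for .5 ties. Apply it at baseline and at every post-baseline visit, for the success rule and the categorical table alike. Add two sensitivity analyses: one using the unrounded average with a cut at 1 or below, and one without version 1.0 subjects.
2. Round each imputed IGA to the nearest grade within 0-4 before classifying it, which puts the success cut at below 1.5.
3. Set NIMPUTE to 50 in the first PROC MI call, to match the text.
4. Define the roughness and palm/sole responder as at least a 2-grade reduction, in the ITT population, in line with the wording of the primary endpoint.

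The cost is a few SAP sentences, the matching footnotes and a rounding step in the code. Rounding is an approximation and can relax the 2-grade criterion for some version 1.0 subjects. The sensitivity analyses in item 1 would show whether that matters.

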3.4. Treatments Administered

For the Double-blind Treatment Period, a fixed dose (determined at Visit 2) of trifarotene cream HE1 100 µg/g or 200 µg/g or vehicle cream will be applied topically twice weekly on up to 90% body surface area (BSA) of each subject. Trifarotene cream HE1 is a cream containing 100 or 200 µg/g (0.01% [w/w] or 0.02% [w/w], respectively) of CD5789. Vehicle contains the same ingredients, without the CD5789. Trifarotene cream HE1 and vehicle will be provided in cream form for topical application and will be packaged in 50-g tubes from which up to 36 g of investigational product (IP) may be dispensed per application, i.e., the maximum dose per

application. Study staff will apply the first dose of study drug to each subject in the clinic on Day 1 after baseline measurements, and will record the amount of study drug applied.

Thereafter, each subject will apply approximately the same amount (up to 36 g) of study drug as for the first dose on up to 90% of BSA twice weekly, sparing the scalp, inguinal, and axillary areas. Subjects will receive an adequate number of tubes to use 1 tube per application and will use a new tube for each treatment day.

For the OLE, all subjects will receive trifarotene cream HE1 200 µg/g and apply the same fixed dose in the same manner as in the Double-blind Period for an additional 90 days.

If the treatment causes application site reactions, the frequency of application will be reduced or interrupted only on the area of concern, as indicated herein. During all clinic visits, the investigator will assess local tolerability (Scale: 0-3 [none, mild, moderate, severe]) for stinging/burning, pruritus, erythema) for each body area (chest/abdomen, back, arms, legs, and face/neck), and the following procedures will be followed:

- If a score of 2 (moderate) is recorded on a local tolerability assessment scale (stinging/burning, pruritus, erythema) on any treated area, the study drug will be applied on that area only once weekly, until the score is back to <2. Continue to treat all other areas twice weekly provided the score is <2 on those areas.
- If a score of 3 (severe) is recorded on a local tolerability assessment scale (stinging/burning, pruritus, erythema) on any treated area, the study drug will not be applied on that area until the score is back to <3 (i.e., “drug holiday”). Continue to treat all other areas twice weekly provided the score is <2 on those areas.

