- **Intent-to-treat (ITT):** all randomized subjects. This population will be used as the primary population for the analysis of efficacy for the Double-blind Period of the study. Subjects will be analyzed by randomized treatment.
- **Modified intent-to-treat (mITT):** all subjects in the Safety population with at least 1 postbaseline assessment of efficacy in the Double-blind Period. Subjects will be analyzed by randomized treatment.
- **Per-protocol (PP):** subjects in the mITT population who met all inclusion criteria and no exclusion criteria, were compliant with study drug application, and who had no significant protocol deviations. Subjects will be analyzed by actual treatment received.
- **Pharmacokinetic (PK):** all subjects in the Safety population who have at least 1 plasma sample with quantifiable concentration. This population will be used to summarize all PK endpoints. Subjects will be analyzed by actual treatment received.

The following analysis populations are planned for the OLE of this study:

- **OLE Safety:** all subjects who complete the 90-day Double-blind Treatment Period and receive at least 1 application of study drug in the OLE.
- **OLE ITT:** all subjects who complete the 90-day Double-blind Treatment Period and sign the OLE informed consent.
- **OLE mITT:** all subjects in the OLE Safety population with at least 1 assessment of efficacy after Visit 6.
- **OLE PP:** all subjects in the OLE mITT population who met all inclusion criteria and no exclusion criteria, were compliant with study drug application from baseline through EOT, and who had no significant protocol deviations throughout the study.

Since all subjects in the OLE are to receive trifarotene cream HE1 200 µg/g, analyses will be by actual treatment received.

Inclusion in the analysis populations will be determined prior to database lock. Deviations related to COVID-19 will also be evaluated in determining PP population eligibility.

6. General Issues for Statistical Analysis

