7.4. Exposure and Compliance

Compliance by tube weight and compliance by number of doses will be summarized by treatment group using descriptive statistics. The total weight of tubes dispensed and returned, as well as total number of tubes dispensed, returned, and returned unused will also be summarized. This analysis will be conducted for the Safety population and for the OLE Safety population.

A subject is compliant with study product if he or she takes at least 80%-120% of the scheduled doses as assessed by number of doses taken reported, supplemented by tube weight and diary entries. The number and percentage of subjects who were compliant will be tabulated by treatment group for the Double-blind Period and overall for the OLE. Derivations of compliance are defined in Section 6.1.7.

All initial study drug application, drug accountability (dispensed and returned), and subject diary data collected will be listed. Changes in treatment administration or treatment dispensation due to COVID-19 including start and end dates of change, method of alternative administration/dispensation, dosing interruptions, and relevant changes to compliance expectations (weights or tube counts) will be documented from the COVID-19 visit impact log.

8. Efficacy Analysis

All efficacy endpoints will be summarized using the ITT population. The primary analysis will be repeated in the mITT and PP populations.

Summaries of efficacy variables in the OLE will be provided using the OLE ITT. Primary IGA summaries will also be provided for the OLE mITT and OLE PP populations. For continuous efficacy analyses using MMRM, only formal comparisons of change from baseline will be performed in the OLE. No other formal inferential analyses will be conducted for efficacy variables in the OLE.

All efficacy data, regardless of population, will be presented in data listings.

If alternative methods are used for capturing efficacy assessments (i.e., in person not on site at the subject's home, remotely with visual aid, or remotely via telephone), additional sensitivity or subgroup analyses may be performed to assess the potential impact to efficacy analyses. These will be delineated as ad hoc analyses in the CSR.

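### Expected doses are fixed at two per week and counted in tubes, so long all-area reductions or holds made under Section 3.4 score as non-compliance, while partial-area holds leave the count unchanged

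*SAP*

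**What the plan says.** SAP Section 3.4 confines any reduction or interruption to the affected body area. At a score of 2, "the study drug will be applied on that area only once weekly, until the score is back to <2". At a score of 3, "the study drug will not be applied on that area until the score is back to <3". Areas scoring below 2 continue twice weekly, and each application uses one new tube.

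Section 6.1.7 then gives the compliance arithmetic:

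- "Number of expected doses = 2 * number of weeks on study"
- "Number of weeks on study = (last day on study – treatment start date + 1) / 7"
- "Number of doses taken = total number of tubes returned – total number of tubes returned unused"
- "Compliance by number of doses = number of doses taken / number of expected doses * 100" (as a percentage)

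Section 7.4 calls a subject compliant at 80% to 120% of scheduled doses. The dose count is the main source, tube weight and diary are supplements, and the derivations are referred back to Section 6.1.7. For the pandemic, Section 7.4 adds that "relevant changes to compliance expectations (weights or tube counts) will be documented from the COVID-19 visit impact log". It has no counterpart for changes required by Section 3.4.

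Under Section 5, PP subjects are those who "were compliant with study drug application, and who had no significant protocol deviations". The open-label extension PP set (OLE PP) carries a similar condition, from baseline through end of treatment. Under Section 8 the primary analysis is repeated in PP.

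**The concern.** The plan tells subjects to apply less cream when they react and then measures compliance against a schedule that assumes they never do. The mismatch works in two directions, and in different subjects.

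When all treated areas are reduced or held, fewer tubes are used against an unchanged denominator. A subject who did what Section 3.4 requires can fall below 80%, and PP membership then depends on a post-randomisation reaction to the cream.

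When only some areas are affected, a tube is still opened at each application. The count stays near 100% however little of the body is treated, and the subject enters the PP analysis as fully exposed.

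At stake is the meaning of the compliance tables and the PP repeat of the primary analysis. With 65 subjects enrolled (about 65/3 = 22 per arm), a few misclassified subjects would be a visible share of an arm.

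**Working it through.** The plan states no compliance result to reproduce, so the check applies its own formulas.

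**Inputs.** Two doses per week, weeks on study and doses taken as used tubes come from Section 6.1.7. The 80% lower limit comes from Section 7.4. One tube per application and the area rules come from Section 3.4. The Day 90 window of 83 to 97 days comes from Table 3, and visit days from Table 1.

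**Limits at 90 days.**
- Expected doses: 2 × 90/7 = 25.71
- 80% limit: 0.80 × 25.71 = 20.57, so at least 21 tubes
- Doses that may be lost: 25.71 − 20.57 = 5.14
- All treated areas once weekly loses 1 dose a week: fails after 5.14 weeks, about 36 days
- All treated areas held loses 2 doses a week: fails after 5.14/2 = 2.57 weeks, about 18 days

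For 83 to 97 days these limits become 4.74 to 5.54 weeks and 2.37 to 2.77 weeks. If OLE PP compliance is computed once over 180 days, expected doses are 2 × 180/7 = 51.43 and the allowance is 10.29, so the limits double to about 72 and 36 days.

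**Scenarios over 90 days, with all treated areas affected.**

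| Pattern | Doses lost | Compliance | Result |
|---|---|---|---|
| Held for 2 weeks | 4.00 | 84.4% | passes |
| Once weekly, Day 30 to 60 | 30/7 = 4.29 | 21.43/25.71 = 83.3% | passes |
| Held 2 weeks, then once weekly 2 weeks | 4 + 2 = 6.00 | 19.71/25.71 = 76.7% | fails |
| Once weekly, Day 14 to 60 | 46/7 = 6.57 | 19.14/25.71 = 74.4% | fails |
| Held, Day 30 to 60 | 2 × 30/7 = 8.57 | 17.14/25.71 = 66.7% | fails |
| Once weekly, Day 30 to 90 | 60/7 = 8.57 | 17.14/25.71 = 66.7% | fails |

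**Scenario with only some areas affected.** No tubes are lost, so compliance is about 100%. If four of the five tolerability areas were held throughout and one was treated twice weekly, the tube count would still be about 100%. Counting areas equally, only 1/5 = 20% of area-applications would have been given.

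**Can the supplements correct this?** Section 7.4 gives no rule for how they alter the result. Tube-weight compliance divides by weight dispensed. With a 36 g maximum from a 50 g tube it cannot exceed 36/50 = 72%, assuming net content weights, so it does not measure adherence to the prescribed schedule. The diary records untreated areas and reasons, but these appear only in Listing 16.2.5.3, and no derivation or table uses them.

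**Which rule decides?** The Table 14.1.5.3 footnotes differ from the text. They put the diary first, and they derive doses taken as tubes dispensed minus tubes returned minus tubes returned unused. As an illustration, take 26 tubes dispensed, all used and all returned. Section 6.1.7 gives 26 − 0 = 26 doses, and the footnote gives 26 − 26 − 0 = 0.

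**The case against.** A reader might infer that subjects who follow the reduction rules generally drop out of PP. The documents do not support that. Reductions act area by area, unaffected areas continue twice weekly, and the tube count is unchanged. Exclusion needs every treated area to be affected, and for a long time. One 30-day visit interval with all areas once weekly still passes. Unscheduled visits are provided for, and a Day 45 telephone contact falls between Day 30 and Day 60, so a reaction need not persist unassessed for the whole interval. This stands and limits how often the problem will arise.

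A reader might also say that area-level holds go unseen. That is too strong. The diary captures and lists untreated areas, tolerability is summarised by body area and visit, and weights used are tabulated. What is missing is any defined use of the area data in measuring exposure or compliance.

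The pandemic wording should not be over-read either. Section 7.4 says changed expectations will be documented. It does not say that the Section 6.1.7 denominator is adjusted for them.

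A further objection is that crediting mandated holds keeps less-exposed subjects in PP. That is true, and it follows from reading PP as adherence to the protocol. Section 5 defines PP by compliance and absence of significant deviations, with no minimum exposure, so that reading fits the plan. The area-level summary is needed to make the lower exposure visible.

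Finally, ITT is the primary efficacy population and PP is labelled a sensitivity analysis. This also stands.

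**Conclusion.** The point holds in a limited form. Section 6.1.7 gives a definite rule that classifies some subjects wrongly: someone who obeyed Section 3.4 on all treated areas for more than about 36 days once weekly, or more than about 18 days held, is scored below 80% in a 90-day period and can be excluded from PP. OLE PP is exposed to the same fault. In the commoner partial-area case the count stays near 100% and says nothing about how much skin was treated.

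The figures assume that the Section 6.1.7 dose count decides compliance, that no doses are missed for other reasons, and that the period is 90 days. The first assumption is itself unsettled, because the Table 14.1.5.3 footnotes say otherwise.

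It is tempting to conclude that PP will be biased in favour of active drug or against the higher concentration. The documents give no rate of all-area reactions and no difference between arms, so neither the direction nor the size of any effect on PP success can be stated. The consequence is limited to the compliance tables and the PP sensitivity analyses; the ITT primary analysis is untouched. It should be corrected before populations are fixed at database lock.

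**What to change.** 1. In Section 6.1.7, define expected (scheduled) doses as two per week minus the applications that Section 3.4 required to be omitted on all treated areas, identified from recorded tolerability scores together with diary reasons. Use this denominator for the 80% to 120% rule in Section 7.4 and for PP and OLE PP. A subject who follows Section 3.4 exactly then scores 100% in every all-area scenario above.
2. Summarise from the diary, by arm, the proportion of area-applications given, so that reduced exposure in subjects kept in PP is visible. The adjusted tube count alone would not show it.
3. Reconcile Sections 6.1.7 and 7.4 with the Table 14.1.5.3 footnotes on which source decides compliance and how doses taken are counted, and state how diary and tube weight enter the decision.

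The cost is SAP wording and programming on data already collected, plus some review of diary reasons before lock. The downside is that PP will include some subjects with lower exposure. The change concerns only how compliance is scored; no dosing rule is proposed or judged.
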